1.1 Metastatic spinal cord compression

Metastatic spinal cord compression (MSCC) is a feared complication of metastases to the vertebra. Approximately 5-10 percent of patients with metastatic cancer experience MSCC, most commonly patients with lung-, breast-, prostate and renal cancer.¹ MSCC is a disabling condition that can lead to pain, disablement of sensory and motor function distal to the injury.² Early detection and onset of treatment is key to improve outcome results. Diagnosis is typically set through either CT or MRI scan; however, MRI is the preferred modality for diagnosing.³ Symptoms are severe, unremitting pain, progressive discomfort, sensory symptoms, function deficits and bladder or bowel dysfunction⁴. Treatment is mainly high dose steroids to decrease edema and radiotherapy. Surgery is offered, when possible, to patients in good performance status and followed by radiotherapy². Interventions mainly aim at pain relief and preserving motor functions. A small fraction of patients with highly chemo-sensitive tumors are offered chemotherapy.⁴ The performance status at the time of diagnosis is the main determining factor of the post-treatment outcomes, with patients with lower-extremity function and sensation at the onset of treatment having a longer survival time⁴. When MSCC is diagnosed, life expectancy is typically short, with a 2-year survival of approximately 10% and a median survival of less than 6 months.^{2,5} As treatment is palliative Quality of Life (QoL) is important, however, patients may experience early toxicity after radiotherapy, paradoxically causing reduced QoL.^{5,6}

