2. To investigate if there is a difference in pain response, weight, primary treatment site re-irradiation, quality of life and overall survival in patients treated with esophagus-sparring radiotherapy compared to patients receiving standard treatment.

3. To describe the dose-response relationship for the esophagus in the palliative dose spectrum.
4. To investigate if esophagus-sparring radiotherapy will increase other toxicities compared to standard radiotherapy.

Primary endpoints

Co-primary endpoints are

- a. Peak patient reported dysphagia (PRO-CTC-AE version 1) within the first five week after treatment start.
- b. Ability to walk, measured by the mobility dimension of the EQ-5D-5L questionnaire.

Secondary endpoints

- Quality of life, measured by EORTC-QLQ-C30 and EQ-5D-5L
- Nausea and dyspepsia measured by PRO-CTC-AE Version 1.0
- Treatment site pain response measured by International Consensus Pain Response Endpoints (ICPRE)
- Patient reported toxicity reported in PRO-CTC-AE-Version 1.0 “Other symptoms” section
- CTC-AE* Version 5: Cough, dyspnea, dyspepsia, dysphagia, hoarseness, oropharyngeal pain
- Changes in weight
- Consumption of corticosteroids, antacids and antiemetics
- Treatment site re-irradiation rate
- Hospitalization rate
- Overall survival

*Registered from patient no. 107

Trial design

The trial is designed as a phase III, randomized, single-blind clinical trial, clinicaltrials.gov ID No. NCT051098.

The trial is performed in a public health care system including two academic cancer centers treating MSCC. The individual centers are started at different times due to logistics. Patients are randomized 1:1 to either esophagus-sparring treatment or standard treatment. Patients are followed actively for 9 weeks after treatment start. Dysphagia, nausea and dyspepsia from the NCI PRO-CTC-AE Version 1.0 library and treatment site pain (Numeric Pain Rating Scale) are reported daily for 5 weeks and subsequently weekly for 4 weeks. Quality of life (EQ-5D-5L and QLQ-C30), use of medication (glucocorticoid, antiemetic, analgesic) and weight are reported weekly for 9 weeks, **Table 1**.

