Table 2: Distribution of ambulatory function. The conventional arm follows the SCORAD trial (Hoskin et al., 2019).

Recruitment, withdrawal, and follow-up

Enrollment, intervention, allocation, follow-up, and data analysis will be summarized in a CONSORT diagram in accordance with CONSORT 2010 guidelines (4)

Statistical principles

Confidence intervals and P values

Level of significance: $p < 0.05$ with no adjustment for multiplicity. Confidence intervals are reported at 95 % limits (bound by zero) and calculated by the binominal distribution for rates and as per Kaplan-Meier method for time-to-event analyses.

Analysis

We will report our data in accordance with the CONSORT 2010 guidelines including the CONSORT Patient-Reported Outcome (PRO) extension (4,5) .

Analyses will be performed per-protocol for all patients who have received any study treatment.

Primary analysis of NCI-PRO-CTC-AE toxicity will only include weeks where ≥ 3 days questionnaires are completed.

Primary analysis of EQ-5D-5L and EORTC-QLQ-C30 will only include completed questionnaires.

All CTC-AE and PRO-CTC-AE grades will be reported.

Missing data will be described in detail, see missing data section.

A. Co-primary endpoints

1. Peak dysphagia (difficulty swallowing) measured by NCI-PRO-CTC-AE within 5 weeks after start of radiotherapy (daily measurements).

PRO-CTC-AE responses are scored from 0 to 4, with 0 representing "None" and 4 representing "Very severe". For each patient the peak value within 5 weeks after start of radiotherapy (daily measurements) will be included in the analysis. Difference in scores between treatment arms will be compared using Wilcoxon rank-sum test.

2. Ambulatory function measured by EQ-5D-5L mobility dimension at 9 weeks after start of radiotherapy.

EQ-5D-5L measures individual generic health status using 5 dimensions: mobility, self-care, usual activities, pain/discomfort, and anxiety/depression. Each dimension has 5 levels depending on the severity of symptoms, with 1 representing “No problems” and 5 representing “Extreme problems”. Difference in scores between mobility dimension treatment arms will be compared using Wilcoxon rank-sum test.

B. Severity of dysphagia, nausea and dyspepsia measured by NCI-PRO-CTC-AE [Time Frame: Week 1-9 after start of radiotherapy (repeated measurement)].

CTC-AE responses are scored from 0 to 4, with 0 representing “None” and 4 representing “Very severe”.

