- The volume of esophagus and posterior pharyngeal wall (% and cm³) receiving more dose than the prescribed constraint
- Selected OAR will be presented (e.g., Spinal Cord D0.027cm³, D0.5cm³, lung V20 and V5)

Double included patients

The ESO-SPARE protocol allowed participants to be included twice at the discretion of the treating oncologist. Double included participants were excluded at the second entry for time-to-event analyses (survival) and the quality-of-life analyses. For radiation details analyses, all lesions will be included.

Missing data

- We will report the numbers and proportions of missing data in each trial arm including:
 - Number of participants who have died.
 - Number of surviving participants with missing data.
 - The proportion of participants with partly completed questionnaires and the proportion of item-level missing data at each timepoint.
- Reasons for missing data will be collected for all randomized patients and reported for each trial arm.
- The assumed missing data mechanism will be reported for all primary and secondary outcome measures. For each outcome missing data will be categorized as.
 - a. Missing completely at random – when missingness is nothing to do with the participant.
 - b. Missing at random – when missingness is related to the participant and can be predicted from other information about them.
 - c. Missing not at random – when missingness is specifically related to the data that are missing.
- We will provide a detailed comparison of the characteristics of those with observed and missing data before and after the interim analysis (1).
- In case of non-complete reporting of measurements, the following assumptions are made:

If the NPRS score is not given, but the patient is described without any pain and take no analgesic medication, the NPRS score is set to zero. All other cases, the NPRS is recorded as “not available”.
- Where missing data is present, secondary sensitivity analysis using multiple imputation and model-based methods assuming that data are missing not at random may be performed.

Statistical software

All statistic calculations will be performed using SPSS (SPSS Inc, Illinois, USA) and R statistics (RCRAN).

Analysis summary

Outcome	Instrument/Method/Unit	Timeframe	Data type	Statistical analysis
Primary Peak dysphagia	NCI-PRO-CTC-AE	Within five weeks after start of radiotherapy	Ordinal	Wilcoxon rank-sum test

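### The week-9 walking co-primary counts only completed questionnaires, so harm acting through death or inability to answer cannot show in that test, and no planned analysis combines death with walking

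*SAP*

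**What the plan says.** SAP, Analysis, item A.2 defines the second co-primary as "Ambulatory function measured by EQ-5D-5L mobility dimension at 9 weeks after start of radiotherapy", and adds: "Difference in scores between mobility dimension treatment arms will be compared using Wilcoxon rank-sum test". The general rules at the head of the same section limit the data: "Primary analysis of EQ-5D-5L and EORTC-QLQ-C30 will only include completed questionnaires". They also set the population: "Analyses will be performed per-protocol for all patients who have received any study treatment". No rank, score or state is given to a patient who has died or has no week-9 form.

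The SAP's sample size section explains what the endpoint is for. It must show that less esophageal toxicity is not bought with a weaker radiation effect, and a deterioration like that in SAP Table 2 would lead to rejection of the experimental treatment. The section enlarges the trial to 100 per arm because of early death and frailty, and powers the walking test on 66 evaluable per arm. Protocol 1.1 gives the prognosis as "a median survival of less than 6 months".

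Mobility is collected more often than it is used: "Quality of life (EQ-5D-5L and QLQ-C30), use of medication (glucocorticoid, antiemetic, analgesic) and weight are reported weekly for 9 weeks". For missing data, the SAP promises counts of deaths and of survivors with missing data by arm, with reasons. Beyond that it says only that "secondary sensitivity analysis using multiple imputation and model-based methods assuming that data are missing not at random may be performed".

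**The concern.** Having a completed week-9 form is an event after randomisation. Protocol 6.4 lets the sparing plan compromise target dose, so the feared harm is loss of neurological function. Protocol 1.1 links better leg function at treatment start to longer survival, so a patient who loses function may well be among those who die or become too ill to answer. If sparing moves patients from walking to dead or unable to respond, they leave both numerator and denominator, and the remaining patients may look alike. This is a selection problem, separate from the number evaluable.

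The week-9 test also makes no use of the mobility item from weeks 1 to 8. The Analysis summary table applies mixed models to the EQ index and VAS; it names no longitudinal model for the mobility item.

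**Working it through.** **Inputs.** SAP Table 2, grades 1 to 4: conventional 22/44/26/8%, experimental 11/32/37/20%. Planned size 100 per arm, 66 evaluable, so implied loss is (100 − 66)/100 = 34%. Alpha is 0.05; sidedness is not stated, so two-sided is assumed. The documents give no week-9 mortality or non-response by arm, so every loss pattern below is an assumption.

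**The plan's own figure.** Multinomial draws from Table 2 with a tie-corrected Wilcoxon test at 66 per arm give 82.9% power (200,000 simulated trials). The stated 84% is reproduced to within two points. One-sided 0.05 would give 89.8% and does not match. Behind the 84% lies the assumption that the 34% lost are unrelated to arm and walking state.

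**Plausible deaths by week 9.** With a constant hazard, the proportion dead is 1 − 0.5^(9/median in weeks). A 6-month median (26 weeks) gives 1 − 0.5^(9/26) = 21%. A 4-month median (17.4 weeks) gives 30%.

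**Effect on the test.** 100 per arm, with a fifth state (dead or no form) either dropped, as in the SAP, or ranked below grade 4.

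| Assumed loss | Lost, conventional v experimental | Completers only | Loss ranked worst |
|---|---|---|---|
| Table 2 harm; loss by grade 10/15/40/70% in both arms | 25% v 35% | 74% | 78% |
| Table 2 harm; loss by grade 5/15/50/85% in both arms | 28% v 41% | 63% | 83% |
| Completers identical, extra loss in experimental arm | 25% v 40% | 5% | 48% |
| Completers identical, extra loss in experimental arm | 20% v 40% | 5% | 72% |
| Table 2 harm; loss unrelated to arm and function | 34% v 34% | 83% | 33% |

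Loss in the first row: conventional 0.22×0.10 + 0.44×0.15 + 0.26×0.40 + 0.08×0.70 = 0.248; experimental 0.11×0.10 + 0.32×0.15 + 0.37×0.40 + 0.20×0.70 = 0.347. With no harm and 34% lost in each arm, both tests reject in about 5% of trials.

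Three further grade-dependent patterns gave 54-71% for completers and 62-83% with loss ranked worst. In one of them the completers test was the stronger (71% v 62%).

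**Living non-responders matter.** In the 25% v 40% case, suppose half the loss is non-fatal, and only death is ranked while living non-responders are left out. Power is then about 24%, not 48%.

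**What the survival test can see.** Deaths of 25% v 40% by week 9 imply a hazard ratio of ln(0.60)/ln(0.75) = 1.78. Log-rank power is Φ(½√d × ln HR − 1.96). With d = 25 + 40 = 65 events, this is about 64%; with an assumed 150 events and a persisting hazard ratio, about 94%.

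**The case against.** A reader might infer that harm through decline and death is invisible to the whole trial. The documents do not support that. SAP items L to N compare hospital days per day alive, and test re-irradiation and overall survival by log-rank. Deaths and survivors with missing data are counted separately by arm. Item J models QLQ-C30 domains, and that questionnaire asks about long walks, short walks and time in bed or a chair. Telephone and paper reporting should reduce loss from illness. Decline in patients who still answer is tested directly.

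The 5% rejection rate also follows from assuming identical completers. That fits poorly with the argument that lost function causes the loss. When loss tracks walking grade, the completers test keeps most of its power.

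Three further inferences go too far. The SAP does not say that walking scores would be imputed for the dead; it leaves this open. Dropping a partly completed form with mobility answered is one reading of the completed-questionnaire rule. The 21-30% dead by week 9 uses the general prognosis, whereas enrolment requires ability to complete questionnaires and admits nerve root compression and epidural ingrowth, so mortality may be lower.

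What stands against the plan is narrower. None of these analyses enters the week-9 test or has a stated bearing on its conclusion, and the log-rank test cannot see a living patient who is too ill to answer.

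**Conclusion.** The concern holds for the walking test itself. It conditions on survival and response, the plan expects about a third of patients to be lost, and the only remedy named for the bias is optional and unspecified. Where loss depends on walking grade, the loss of power against the Table 2 harm is moderate: about 63-74% for completers against 78-83% with loss ranked worst. It is total only in the extreme case of identical completers (5% v 48%). Where loss is unrelated to arm and function, the completers test is much the better (83% v 33%), so it should not be replaced. The powers are illustrative: they rest on assumed losses and on the four-grade Table 2 scale, not the five-level EQ-5D item that will be analysed. This should be fixed, as a cheap strengthening of a co-primary harm test. It does not show that the trial would miss harm.

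**What to change.** Keep the completers test and amend SAP A.2 as follows.

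1. Use every answered week-9 mobility item, whether or not the rest of the form is complete.
2. Make mandatory a supporting Wilcoxon analysis of all treated patients by allocated arm, with death by week 9 ranked below mobility level 5. State the rule for living patients without a form: ranked with level 5 or below in one version, multiply imputed in another.
3. Add a repeated-measures ordinal model of the weekly mobility item while patients are alive, and report its week-9 contrast.
4. State that mobility is not imputed after death.
5. Report deaths and living non-responders by arm beside the result, with effect estimates and confidence intervals for every analysis. Conclude that walking is not compromised only when none of them points to harm. Non-significance of the death-ranked test should not serve as a gate, since that test can have only 33% power.

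The cost is SAP wording and supporting analyses of data already collected: weekly EQ-5D-5L, and survival from treatment records. The downside is that the death-ranked analysis loses power when deaths are unrelated to walking, which is why it is added and not substituted.

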The PRO-CTCAE® items and information herein were developed by the Division of Cancer Control and Population Sciences in the NATIONAL CANCER INSTITUTE at the NATIONAL INSTITUTES OF HEALTH, in Bethesda, Maryland, U.S.A. Use of the PRO-CTCAE® is subject to NCI's Terms of Use.

Health Questionnaire

English version for the UK

Under each heading, please tick the ONE box that best describes your health TODAY.

MOBILITY

I have no problems in walking about	
I have slight problems in walking about	
I have moderate problems in walking about	
I have severe problems in walking about	
I am unable to walk about	

SELF-CARE

I have no problems washing or dressing myself	
I have slight problems washing or dressing myself	
I have moderate problems washing or dressing myself	
I have severe problems washing or dressing myself	
I am unable to wash or dress myself	

USUAL ACTIVITIES (e.g. work, study, housework, family or leisure activities)

I have no problems doing my usual activities	
I have slight problems doing my usual activities	
I have moderate problems doing my usual activities	
I have severe problems doing my usual activities	
I am unable to do my usual activities	

PAIN / DISCOMFORT

[figure not shown]
I have no pain or discomfort	
I have slight pain or discomfort	
I have moderate pain or discomfort	
I have severe pain or discomfort	
I have extreme pain or discomfort	

ANXIETY / DEPRESSION

I am not anxious or depressed	
I am slightly anxious or depressed	
I am moderately anxious or depressed	
I am severely anxious or depressed	
I am extremely anxious or depressed	

- We would like to know how good or bad your health is TODAY.
- This scale is numbered from 0 to 100.
- 100 means the best health you can imagine.
0 means the worst health you can imagine.
- Please mark an X on the scale to indicate how your health is TODAY.

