Data are reported by the patient in a paper-edition trial diary, by electronic questionnaires or by telephone consultations. Survival data, re-irradiation, and hospitalization data are derived from patient's treatment records. After the results of an interim analysis revealing low compliance (1), weekly CTC registrations were implemented for all patients in the first 5 weeks after treatment start (from patient No. 107).

Table 1. Follow-up schedule in the ESO-SPARE trial

	Treatment start	Daily	Weekly	Weekly
		1-5 weeks	1-5 weeks	1-9 weeks
PRO-CTC-AE: Dysphagia, nausea, dyspepsia	X	X		
CTC-AE 5.0*	X		X	
EORTC-QLQ-C30 and EQ-5D-5L	X			X
Medication: Analgesics, corticosteroids, antiemetics	X			
Weight	X			X

*Starting from patient No. 107

Estimated Enrollment: 200 patients.

Allocation: Patients are randomized 1:1 to either esophagus-sparring treatment or standard treatment. Patients are stratified by center and fractionation. Randomization is performed in REDCap using random allocation with a block size of four and six.

Masking: Single-blind. Patients are blinded to randomization outcome.

Study Start Date: May 2021

Estimated Primary Completion Date: April 2024

Study Completion Date: The last patient will be included on April 30, 2024, or after the inclusion of 200 patients, whichever comes first.

Timing of final analysis

Following study closure, nine weeks of follow-up after radiotherapy start will be allowed for all patients, at which point data will be collected for primary end-point analysis. Analysis of data in respect to secondary endpoints and exploratory studies might be analyzed at any point of time, at the discretion of the study group.

Data

Data are captured in REDCap. Data will be kept in databases 10 years after the last patient is included.

[Sample size](#)

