We assume that we can decrease maximum esophageal dose from 30 Gy to 10 Gy and that this will result in a 50% decrease in risk of early esophageal toxicity. We want to conduct a phase III trial with 1:1 randomization between standard VMAT and experimental esophageal VMAT. Prior data (2) indicate that the rate of early esophageal toxicity with standard VMAT is 0.6. If the true early esophageal toxicity rate in the esophagus sparing VMAT arm is 0.3, conventional power calculation indicates that we would need to include 62 patients in each arm, to be able to reject the null hypothesis that the toxicity rates for experimental and control arms are equal with a probability (power) of 0.9. The Type I error probability associated with the test of this null hypothesis is 0.05 and calculations are performed assuming Fisher's exact test. However, with this patient population we anticipate high rate of heterogeneity, and we need to account for loss of follow-up due to patients dying early or being too frail. We increase the study size to 100 patients in each arm to account for these challenges. Patients will be stratified according to fractionation scheme and treating center.

Ambulatory function as a co-primary endpoint

We wish to demonstrate that the improvement in esophageal toxicity does not come at a price of reduced effect of the radiation. As a prioritized secondary endpoint, we choose ambulatory function (preserved ability to walk) measured on a 4-point scale. We assume that the conventional arm follows the distribution of the SCORAD trial and test our ability to detect a difference from an assumed inferior experimental arm in terms of ambulatory function, see Table 2.

If the underlying “true” distribution on ambulatory grades is as depicted in the table and we assume 66 patients per arm are evaluable, we find that 84% of simulated trials would lead to statistically significant differences detected with a Wilcoxon rank sum test for comparing the trial arms. In other words, the power of the trial is enough to detect a deterioration according to the able, which would lead to rejection of the experimental treatment.

The power of ESO-SPARE is enough to detect a difference in ambulatory function as seen in Table 2

	Conventional arm	Experimental arm
Grade 1: Ambulatory without the use of walking aids	22	11
Grade 2: Ambulatory with walking aids	44	32
Grade 3: Unable to walk	26	37
Grade 4: Absence or flicker of motor power in any muscle group	8	20

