Primary Ambulatory function	EQ-5D-5L mobility dimension	At nine weeks after start of radiotherapy	Ordinal	Wilcoxon rank-sum test
Severity of dysphagia, nausea, and dyspepsia	NCI-PRO-CTC-AE	Weekly, week 1-9 after start of radiotherapy	Ordinal, repeated measurement	Generalized Linear Mixed Models
Duration of dysphagia, nausea, and dyspepsia	NCI-PRO-CTC-AE	Within five weeks after start of RT (daily measurements) and at 6, 7, 8, and 9 weeks	Continuous, mean [range]	Descriptive graphical presentation and Wilcoxon rank-sum test for group comparison
Severity of cough, dyspnea, dyspepsia, dysphagia, hoarseness, oropharyngeal pain	NCI-CTC-AE	Weekly, week 1-5 after start of radiotherapy	Ordinal, repeated measurement	Generalized Linear Mixed Models
Duration of cough, dyspnea, dyspepsia, dysphagia, hoarseness, oropharyngeal pain	NCI-CTC-AE	Weekly, week 1-5 after start of radiotherapy	Continuous, mean [range]	Descriptive graphical presentation and Wilcoxon rank-sum test for group comparison
Pain response, severity	ICPRE score	Weekly, week 1-9 after start of radiotherapy	Ordinal, repeated measurement	Generalized Linear Mixed Models

Quality of life	EQ-5D-5L	Weekly, week 1-9 after start of radiotherapy	Categorical (index), and Visual analog scale (continuous)	As per described in EQ-5D-5L guidelines (7) Combined index is calculated using Denmark as reference. Changes in EQ-index value and VAS-score over time (repeated measurement) will be analyzed with Generalized Linear Mixed Models.
Quality of Life	EORTC-QLQ-C30	Weekly, week 1-9 after start of radiotherapy	Categorical (raw QLQ-C30 scores) and Continuous (the raw QLQ-C30 scores can be transformed to scores ranging from 0 to 100)	As per described in EORTC-QLQ-C30 guidelines (8). Descriptive statistics of QLQ-C30 domains and analysis of changes over time with Generalized Linear Mixed Models
Weight	Change in kg from baseline	Weekly, week 1-9 after start of radiotherapy	Continuous, repeated measurement	Linear Mixed Effects Models
Hospitalization rate	Days hospitalized of days alive (absolute numbers and %)	Week 1-9	Continuous, mean [range]	Wilcoxon rank-sum test
Re-irradiation rate, primary site	Number of patients receiving re-irradiation in each arm (absolute numbers and %)	3, 6- and 12-months after inclusion	Continuous, mean [range]	Wilcoxon rank-sum test

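### The week-9 mobility test, the trial's check for harm, leaves out baseline mobility; adjusting for it would detect the plan's own deterioration more often with data already scheduled

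*SAP*

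**What the plan says.** The second co-primary endpoint is the EQ-5D-5L mobility item at week nine, scored on five levels. SAP Analysis A.2 gives the whole method in one sentence: "Difference in scores between mobility dimension treatment arms will be compared using Wilcoxon rank-sum test". The row "Primary Ambulatory function" in the Analysis summary repeats the test. Neither place names a covariate or stratum.

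The item is also scheduled at baseline. SAP Table 1 marks "EORTC-QLQ-C30 and EQ-5D-5L" at treatment start and weekly to week nine, and Protocol Table 2 marks EQ-5D-5L at baseline.

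SAP Analysis item I plans mixed models for quality-of-life scores over time. For EQ-5D-5L the Analysis summary specifies the index value and the VAS; the mobility item is not named.

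On power, the SAP section on ambulatory function assumes 66 evaluable patients per arm and reports: "we find that 84% of simulated trials would lead to statistically significant differences detected with a Wilcoxon rank sum test". A deterioration of the size in its Table 2 is one "which would lead to rejection of the experimental treatment".

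On the analysis set, the SAP says: "Primary analysis of EQ-5D-5L and EORTC-QLQ-C30 will only include completed questionnaires".

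**The concern.** The mobility test is there to show that sparing the esophagus is not paid for with a weaker radiation effect. A missed deterioration is therefore the costly mistake: the trial would report less dysphagia and no visible loss of walking. The endpoint is framed as keeping the ability to walk, yet the test ignores where each patient started.

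Protocol 1.1 names performance status at diagnosis as the chief determinant of outcome after treatment, so baseline mobility probably predicts week-9 mobility. Randomization does not balance it either: Protocol 3.5 and the SAP stratify by center and fractionation only. When baseline predicts outcome, leaving it out lets differences between patients at entry act as noise in the comparison.

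**Working it through.** **Inputs from the documents.** SAP Table 2, grades 1 to 4: conventional 22/44/26/8%, experimental 11/32/37/20%. 66 evaluable per arm, 1:1 allocation, significance level 0.05. Sidedness is not stated; two-sided is the version that reproduces the stated power (one-sided gives 89.9%).

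**Inputs assumed.** The baseline-to-week-9 correlation on a latent normal scale is not in the documents, so 0 to 0.7 is shown. Baseline has the conventional-arm distribution. Fractionation (40% single fraction) and center (50/50) are unrelated to outcome.

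**1. Reproduce the stated 84%.**
- The chance that a random experimental patient is worse than a random control patient is 0.32×0.22 + 0.37×0.66 + 0.20×0.92 = 0.4986.
- The chance of a tie is 0.22×0.11 + 0.44×0.32 + 0.26×0.37 + 0.08×0.20 = 0.2772.
- The Wilcoxon effect is 0.4986 + 0.2772/2 = 0.637, which is 0.137 from no effect.
- Pooled proportions are 0.165, 0.38, 0.315 and 0.14, and their cubes sum to 0.093. The null SE is √[(1 − 0.093)/12 × 2/66] = 0.0478.
- z = 0.1372/0.0478 = 2.87, and power ≈ Φ(2.87 − 1.96) = 82%.

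Simulating the tie-corrected test (60,000 trials) gives 82.9%, with 4.96% under the null. The SAP's 84% is reproduced to within about a point.

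**2. Add baseline.** Latent correlations of 0.3, 0.5 and 0.7 give observed rank correlations r of 0.255, 0.429 and 0.609. Adjustment shrinks the residual variance by about 1 − r², so z becomes 2.867/√(1 − r²) = 2.97, 3.17 and 3.61. Power is then Φ(1.01), Φ(1.21) and Φ(1.65), or about 84%, 89% and 95%. Simulation agrees:

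| Latent correlation | Plain Wilcoxon | Rank ANCOVA (baseline, fractionation, center) | Proportional odds, same covariates |
|---|---|---|---|
| 0 | 82.9% | 82.4% | 83.1% |
| 0.3 | 82.9% | 85.0% | 85.0% |
| 0.5 | 82.9% | 89.5% | 89.4% |
| 0.7 | 82.9% | 95.5% | 95.8% |

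The rank ANCOVA figures use 6,000 trials per case; its type I error is 5.0-5.1%. The proportional-odds figures use 4,000 trials per case; the Wald test's type I error is 5.2-5.7%. A repeat of the rank ANCOVA without the strata, with 10,000 trials per case, gave 82.7%, 84.3%, 89.7% and 95.3%. The strata add about 0-1 point and are not the source of the gain.

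**3. Gain in patients.** To match the adjusted test, the plain test would need about 70, 80 and 104 evaluable per arm at 0.3, 0.5 and 0.7. The formula 66/(1 − r²) gives 71, 81 and 105.

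**4. Five levels.** Table 2 has four grades, whereas the EQ-5D-5L item has five, the lowest being "I am unable to walk about". Assume grades 3 and 4 both map to that level, and grades 1 and 2 spread over the rest (11/11/22/22/34% v 5.5/5.5/16/16/57%). The plain test then has 76% power and the adjusted test 78%, 83% and 91-92%.

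**5. Missing baselines.** On four grades with 20% of baselines missing at random, dropping those patients gives 75.8%, 81.6% and 90.1% at 0.3, 0.5 and 0.7. At 0.3 and 0.5 that is below the plain test. Keeping them with a missing-baseline indicator gives 84.4%, 87.9% and 93.1%. Results are nearly the same when worse baselines are missing more often. On five levels with 20% missing and kept, the adjusted test has 78%, 82% and 89%, against about 77% for the plain test.

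**6. Other checks.** A baseline better or worse than the conventional week-9 distribution moves the adjusted figures by about 1 point or less. A Wilcoxon test on change from baseline is not a substitute: it has 66.9% power at 0.3 and 79.0% at 0.5.

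**The case against.** The plan contains no defect on this point. The test is valid and meets the power it was simulated for. The gain rests on a correlation that the documents do not give. It could be modest: baseline is recorded at planning, often on high-dose steroid and sometimes after decompressive surgery. The larger gains are for the four-grade scale and not the planned item; on five levels with 20% of baselines missing, the gain at 0.3 is about 1 point.

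Changing a co-primary test late also carries risk. The SAP follows an interim analysis, only patients are blinded, and secondary endpoints may be analyzed at any time. Nor does adjustment turn a non-significant superiority test into evidence of no harm, or deal with deaths before week nine.

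Most of this stands as a limit on the size and urgency of the point. It does not remove the point: the gain is positive for any plausible correlation above about 0.2, the cost at zero is about half a point, and the change needs no new data. The timing objection is met by fixing the change before any comparison of the arms and keeping the plain test as a named analysis. The no-harm and death issues are separate.

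**Conclusion.** The concern holds as an inexpensive improvement that should be made, not as an error in the plan. With 66 per arm and Table 2, baseline adjustment adds about 2, 7 or 13 points of power at assumed latent correlations of 0.3, 0.5 or 0.7. On the assumed five-level mapping the gain is about 2, 7 or 15 points from a lower start of 76%. Below a correlation of about 0.2 the gain is negligible.

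The figures rest on a latent-normal model, on Table 2 carrying over to the EQ-5D-5L item, and on most baseline forms having been completed. Confidence in the size is medium, because the correlation is unknown. No material gain is claimed for peak dysphagia: with an assumed 85% symptom-free at baseline, adjustment changes power by −1, +1 and +2 points at correlations 0, 0.3 and 0.5.

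**What to change.** Before the arms are compared, amend SAP Analysis A.2 and the Analysis summary as follows.

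- **Primary test:** rank ANCOVA of the ranked week-9 level on arm, ranked baseline mobility, fractionation (single v multi-fraction if levels are sparse) and center.
- **Estimate:** common odds ratio with 95% CI from a proportional-odds model with the same covariates.
- **Supportive:** the plain Wilcoxon test, named as such.
- **Missing baseline:** the patient stays in; set the baseline to a constant and add a missing-baseline indicator. The completed-questionnaires rule should say that it does not exclude patients who lack only the baseline form.
- **Strata:** use those actually programmed. Protocol 3.5 and the SAP agree on fractionation and center; Protocol 3.3 names performance status instead of center and is out of step.
- **Timing:** record that no comparison of mobility by arm preceded the change. If that cannot be shown, keep the plain test as primary and report the adjusted analysis as supportive.

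The cost is SAP wording and a few lines of R. The odds ratio becomes conditional on baseline: about 2.7, 3.0 and 3.7 at 0.3, 0.5 and 0.7, against 2.6 at zero. Its standard error does not shrink. The estimate relies on proportional odds, which Table 2 roughly satisfies: (22/78)/(11/89) = 2.28, (66/34)/(43/57) = 2.57 and (92/8)/(80/20) = 2.88. The rank ANCOVA test does not rely on it. Because the test and the interval come from different methods, the SAP should state that the rank ANCOVA p-value decides.
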